3.2. RANDOMIZATION AND BLINDING

This is an open label, non-randomized study; therefore, blinding considerations are not applicable.

3.3. HANDLING OF DATA

3.3.1. Strata and Covariates

No adjustments will be made for strata.

3.3.2. Examination of Subject Subsets

Analyses of the mITT population will be summarized by cohort at study entry and an overall CIS group.

To assess consistency of efficacy endpoints, the primary and secondary efficacy analyses will be performed for the following subgroups:

- Age ($<75, \geq 75$)
- Gender (Male, Female)
- Region (US, Canada)
- Race (White, Black/African American, Asian, Other)
- Number of prior BCG therapies ($\leq 2, > 2$)
- Number of prior BCG instillations ($\leq 9, \geq 10$)

In each subgroup, CR rate and the associated 95% CI will be calculated, and median values and associated 95% CIs will be calculated for all time-to-event endpoints for the appropriate cohort (EFS, cystectomy-free days, time to disease recurrence, time to progression, PFS, and OS). Results will be displayed in forest plots and Kaplan-Meier curves when indicated.

Adverse events will also be analyzed by subgroup (adverse events, serious adverse events, treatment-related adverse events treatment-related, serious adverse events, and Grade 3 or higher adverse events).

3.3.3. Multiple Testing and Comparisons

All analyses will be conducted without adjustments for multiple comparisons.

3.3.4. Missing Data and Outliers

Every effort will be made to obtain required data at each scheduled evaluation from all subjects who have been enrolled.

See section 3.3.5 for details of imputing missing dates. Unless otherwise specified, all other missing data will not be imputed.

3.3.5. Imputation of Incomplete Dates

An incomplete date occurs when the exact date an event occurred or ended cannot be obtained from a subject. The database contains data fields for month, day, and year. A date is incomplete if at least one of these three fields is not known. For many of the planned analyses, a complete date is necessary in order to determine if the event should be included in the analysis (i.e., if the event is treatment-emergent) or to establish the duration of an event. In such cases, incomplete dates will be imputed.

For purposes of imputation of dates for adverse events and concomitant medications, the start and stop dates of study drug will be utilized to impute missing event start and stop dates. All events with an incomplete start/onset date are assumed to have started at the initiation of the study drug. All events with an incomplete end/resolution date are assumed to have ended on the last date of study drug. The missing or incomplete dates will be imputed using the algorithm described in Table 1.

In an effort to minimize bias, the project statistician will impute missing or incomplete dates from forms other than the adverse events or concomitant medications in a systematic, reasonable manner. In these cases, missing date portions will be imputed using available data as described in Table 2.

Table 1. Algorithm for Imputing Missing/Incomplete Onset or Resolution Dates for Adverse Events or Concomitant Medications

Description of Missing/Incomplete Data Piece	Algorithm	Example
Completely Missing Start Date	Use Study Drug Start Date	Original Event Start Date = " " Study Drug Start Date = "04-16-2014" Imputed Event Start Date = "04-16-2014"
Incomplete Start Date - Missing Day Part	Use Day Part of Study Drug Start Date	Original Event Start Date="04- -2014" Study Drug Start Date="04-16-2014" Imputed Event Start Date="04-16-2014"
Incomplete Start Date - Missing Day/Month Part	Use Day/Month Part of Study Drug Start Date	Original Event Start Date="2014" Study Drug Start Date="04-16-2014" Imputed Event Start Date="04-16-2014"
Completely Missing Stop Date	Use Study Drug Stop Date	Original Event Stop Date = " " Study Drug Stop Date = "04-16-2014" Imputed Event Stop Date = "04-16-2014"
Incomplete Stop Date - Missing Day Part	Use Day Part of Study Drug Stop Date	Original Event Stop Date="04- -2014" Study Drug Stop Date="04-16-2014" Imputed Event Stop Date="04-16-2014"
Incomplete Stop Date - Missing Day/Month Part	Use Day Part of Study Drug Stop Date	Original Event Stop Date="2014" Study Drug Stop Date="04-16-2014" Imputed Event Stop Date="04-16-2014"

Table 2. Algorithm for Imputing Missing/Incomplete Dates Not on the Adverse Events or Concomitant Medications CRF Pages

Description of Missing/Incomplete Data Piece	Algorithm	Example
Completely Missing Date	Use CRF Visit Date, if available	Original Date = " " CRF Visit Date = "04-16-2014" Imputed Date = "04-16-2014"
Incomplete Date - Missing Day Part	Use Day Part of CRF Visit, if available	Original Date="04- -2014" CRF Visit Date="04-16-2014" Imputed Date="04-16-2014"
Incomplete Date - Missing Day/Month Part	Use Day/Month Part of CRF Visit, if available	Original Date="2014" CRF Visit Date="04-16-2014" Imputed Date="04-16-2014"

If the CRF Visit Date is not available, dates of related assessments may be used to determine the date of the assessment. For instance, missing dates for the centrally read pathology or centrally read cytology results where there is not a corresponding visit date for the given visit, the date of the TURBT or date of the cystoscopy associated with the biopsy for the visit will be substituted.

A list of incomplete and imputed dates will be prepared by the project statistician or statistical programmer(s) and will be submitted for review by the sponsor.

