### 15.2 Adverse Events

An adverse event (AE) is defined as any untoward medical occurrence in a subject administered a pharmaceutical product and which does not necessarily have to have a causal relationship with this treatment. An AE can, therefore, be any unfavorable and unintended sign (that may include an abnormal laboratory finding), symptom, or disease temporally associated with the use of a medicinal product, whether or not related to the medicinal product. Any worsening of the subject's pre-existing medical conditions will also be considered an AE, unless it is within the normal range of disease fluctuation for that subject. Pre-existing medical conditions that are stable or improve during the study will be recorded as an AE but will not be considered as treatment-emergent adverse events (TEAEs).

The investigator is responsible for reviewing all laboratory results obtained after a subject signs the ICF through 30 days after the last dose of study drug, whether required by this protocol or for other reasons e.g., evaluation of a pre-existing condition, evaluation and management of an AE. Any abnormal value that leads to a change in the subject's management (e.g., dose interruption, dose reduction, the addition of medication, other medical intervention (e.g., blood transfusion), or increased monitoring) or considered by the investigator to be of clinical significance should be recorded as an AE/SAE.

"Progressive disease" should not be recorded as an AE or SAE. Instead, the diagnoses/syndromes, signs, and/or symptoms associated with a subject's disease progressive should be recorded as AEs, or SAEs if they meet the SAE definition.

All AEs will be assessed using the NCI-CTCAE (version 4.03)  
([http://evs.nci.nih.gov/ftp1/CTCAE/CTCAE\\_4.03\\_2010-06-14\\_QuickReference\\_8.5x11.pdf](http://evs.nci.nih.gov/ftp1/CTCAE/CTCAE_4.03_2010-06-14_QuickReference_8.5x11.pdf)).

AEs for which no appropriate CTCAE term exists will be recorded verbatim from the investigator and graded for severity based on CTCAE definitions:

- Grade 1: Mild; asymptomatic or mild symptoms; clinical or diagnostic observations only; intervention not indicated.
- Grade 2: Moderate; minimal, local or noninvasive intervention indicated; limiting age-appropriate instrumental activities of daily living (ADLs)\*.

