3.3.7. Definitions and Terminology

Adverse Event

An adverse event (AE) is defined as any unfavorable and unintended sign (including an abnormal laboratory finding), symptom or disease temporally associated with the use of a medical treatment or procedure regardless of whether it is considered related to the medical treatment or procedure (attribution of unrelated, unlikely, possible, probable, or definite).

Any medical condition that is present at the time the subject is screened, but does not deteriorate, should not be reported as an AE. However, if it deteriorates at any time during the study it should be recorded as an AE. Hospitalization for elective treatment of a preexisting condition that did not worsen from baseline is not considered an AE or serious AE (SAE).

The descriptions and grading scales found in the revised National Cancer Institute Common Terminology Criteria for Adverse Events (NCI-CTCAE) version 4.03 will be utilized for AE reporting.

Serious Adverse Event

A serious adverse event is any AE that is fatal, life-threatening, requires or prolongs hospital stay, results in persistent or significant disability or incapacity, results in a congenital anomaly or birth defect, or is an otherwise important medical event.

Treatment-emergent AE

Treatment-emergent AEs (TEAEs) are all AEs occurring on or after the date of first dose of study drug through 30 days post the last dose of study drug.

Baseline Value

For purposes of analysis, the baseline value is defined as the last value obtained prior to the first dose of Vicinium.

Study Drug

For the purposes of this study, the term study drug refers to Vicinium.

Day 1 (Baseline)

Day 1 is the day that the first dose of Vicinium is received.

Age

The age of a subject is defined as (Date of Informed Consent – Date of Birth + 1)/365.25.

Study Day

Study Day is defined relative to Baseline (Day 1). Thus, the study day of an event is calculated as:

$$\text{Study Day} = \text{event date} - \text{date of Day 1} + 1.$$

Change from Baseline

Change from baseline for a given endpoint is defined as the Study Day X value minus the Baseline Value.

Cohort 1 Subjects

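### SAP 3.3.5 gives two conflicting rules for incomplete AE onset dates; the Table 1 version can push a real treatment-emergent event outside the TEAE window

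*SAP*

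**What the plan says.** SAP 3.3.5 covers AE and concomitant-medication dates in a paragraph and in Table 1.

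- **Onset, paragraph:** "All events with an incomplete start/onset date are assumed to have started at the initiation of the study drug".
- **Onset, Table 1:** a blank date takes the first-dose date. With the day missing: "Use Day Part of Study Drug Start Date". With day and month missing: "Use Day/Month Part of Study Drug Start Date". The recorded month or year is kept.
- **Stop, paragraph:** "All events with an incomplete end/resolution date are assumed to have ended on the last date of study drug". Table 1 sets a blank stop to the last dose. For a year-only stop its algorithm reads "Use Day Part of Study Drug Stop Date", but its example fills in both day and month.
- **Scope:** "An incomplete date occurs when the exact date an event occurred or ended cannot be obtained from a subject". Ongoing events are not mentioned.

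SAP 3.3.7 defines a TEAE by date alone, from first dose "through 30 days post the last dose of study drug". SAP 5.3.1 applies the 3.3.5 imputation to decide which events are treatment-emergent, and tabulates TEAEs by phase (induction, maintenance).

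On stable pre-existing conditions, Protocol 15.2 says "Pre-existing medical conditions that are stable or improve during the study will be recorded as an AE but will not be considered as" TEAEs. SAP 3.3.7 says that a condition present at screening which does not deteriorate should not be reported as an AE at all.

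**The concern.** Two programmers could each follow SAP 3.3.5 faithfully and produce different TEAE tables, and neither result is satisfactory. In a single-arm trial the TEAE tables are the main safety result. SAP 5.3.1 takes the worst case when severity or relationship is missing. The Table 1 onset rows depart from that principle, because they can place a true on-treatment onset after the window closes. In the other direction, both rules can date an onset before first dose to Day 1, and the SAP's date-only TEAE definition then counts it.

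**Working it through.** **1. The SAP's own examples.** Table 1 uses first dose 16 Apr 2014 and onsets recorded as blank, Apr 2014 and 2014. Applied literally, all three become 16 Apr 2014, as printed. Every example shares the month and year of first dose, so the paragraph and the table agree there and the conflict does not show.

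**2. A case where they differ.**
- First dose 16 Nov 2016, last dose 77 days later: 1 Feb 2017.
- TEAE window ends 1 Feb 2017 + 30 days = 3 Mar 2017.
- An AE recorded only as 2017:
  - Paragraph: 16 Nov 2016, Day 1, a TEAE.
  - Table 1: 16 Nov 2017, study day 365 + 1 = 366, not a TEAE.

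If the true onset was on or before 3 Mar 2017, Table 1 has removed a real TEAE.

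A missing day does less harm. With first dose 17 Oct 2016, last dose 2 Jan 2017 and true onset 20 Jan 2017, a missing day gives 17 Jan 2017 and the event is kept. Loss is possible only near the end of the window. With first dose 28 Oct 2016 and last dose 13 Jan 2017 (window end 12 Feb 2017), a true onset of 5 Feb 2017 becomes 28 Feb 2017 and is lost.

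**3. Share of true TEAEs lost under Table 1, given a partial date.** Assumptions: first doses spread evenly over two years from August 2015; last dose on the first day of the stated week, so study day L = 7 × week − 6; true onset uniform over a window of W = L + 30 days.

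For W ≤ 365, a year-only onset is lost exactly when it falls in the next calendar year. For an onset on window day d, the chance of that is (d − 1)/365. Averaging over d gives (W − 1)/(2 × 365):
- Week 12: 107/730 = 14.7%
- Week 26: 205/730 = 28.1%
- Week 39: 296/730 = 40.5%

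Enumerating every start and onset day gives:

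| Last dose, week | W (days) | Year-only, lost | Day missing, lost |
|---|---|---|---|
| 12 | 108 | 14.7% | 3.9% |
| 26 | 206 | 28.0% | 4.1% |
| 39 | 297 | 40.5% | 2.8% |
| 52 | 388 | 0.2% | 2.1% |
| 65 | 479 | 3.7% | 1.7% |
| 78 | 570 | 10.0% | 1.4% |
| 91 | 661 | 18.0% | 1.1% |
| 104 | 752 | 0.1% | 1.0% |

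The year-only loss falls to almost nothing at weeks 52 and 104 because the first or second anniversary then lies inside the window. Blank dates lose nothing. Under the paragraph the loss is 0% throughout. With the day missing, about 1% of borrowed days do not exist in the recorded month, such as day 31 in a 30-day month.

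**4. Phase.** Under the paragraph, 100% of incompletely dated maintenance-phase onsets are placed on Day 1 and so in induction.

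**5. Pre-dose onsets that become TEAEs under Table 1**, with onset uniform over the stated interval before first dose:

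| Interval before first dose | Day missing | Year-only | Blank |
|---|---|---|---|
| 56 days | 26.3% | 92.2% | 100% |
| 365 days | 4.0% | 49.9% | 100% |
| 730 days | 2.0% | 25.0% | 100% |

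These are the onsets that are blank or share first dose's month (day missing) or year (year-only). An earlier recorded month or year stays pre-dose. Under the paragraph, 100% of incompletely dated onsets go to Day 1.

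**6. Stop dates.** An AE that starts in the 30 days after the last dose and has a blank stop would, read literally, end before it began. Those 30 days are 30/108 = 27.8% of the window with last dose in week 12, and 30/752 = 4.0% in week 104.

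**The case against.** The best defence is rarity. AEs are assessed before and after every instillation (Protocol 10.3, 10.5.1) and again 30-37 days after the last dose (10.6), so an on-treatment event whose month is unknown should be uncommon. The likelier gap is a missing day, which loses only about 1-4%. There are also safeguards: a list of incomplete and imputed dates goes to the sponsor (SAP 3.3.5), all AEs are listed by subject (5.3.1), and listings show partial dates as recorded (section 9). A misclassified event leaves a table but stays visible. All of this stands and limits the size. It does not settle which rule applies.

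Three stronger readings are tempting, and the documents do not support them.

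- **That any incomplete onset can lose a TEAE.** The paragraph loses none. The anniversary shift affects only year-only dates in a calendar year other than that of first dose.
- **That stable pre-existing conditions generally become TEAEs.** They must first be recorded as AEs, on which Protocol 15.2 and SAP 3.3.7 disagree, and the SAP says it supersedes the protocol. Under Table 1 the onset must also be blank or share first dose's month or year.
- **That ongoing toxicity will be reported as resolved.** The SAP's definition of an incomplete date concerns dates that cannot be obtained, and an ongoing event has not ended. No AE duration or resolution table is planned, and TEAE status does not use the stop date. The missing exemption is a wording gap with no planned output shown to depend on it.

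**Conclusion.** The point holds for onset dates. SAP 3.3.5 states two incompatible rules, and treatment-emergence depends on which is programmed. The paragraph keeps every TEAE but assigns incompletely dated maintenance events to induction. Table 1 can drop real TEAEs. Given a year-only date, the loss is about 15%, 28% and 40% with last dose in week 12, 26 and 39, near zero at week 52 or 104, and between those levels otherwise. Given a missing day, it is about 1-4%, with about 1% impossible dates. These figures rest on evenly spread start dates and uniform onset. They are shares of partially dated events, not of all AEs. The documents do not give the number of partial dates, so the total effect is unknown and is probably small.

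Both rules can also count some pre-dose onsets as TEAEs, so the net direction of error in the TEAE count is not known. The disagreement between Protocol 15.2 and SAP 3.3.7 on stable pre-existing conditions is a related inconsistency that needs reconciling.

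**What to change.** 1. Delete the paragraph's sentence on incomplete onset dates, so that one rule remains.
2. Replace the Table 1 onset rows with the earliest date that fits the recorded parts and is not before first dose. For a true TEAE this date lies between first dose and the true onset, so none is lost and no impossible date arises. In the example, an AE dated 2017 becomes 1 Jan 2017, inside the window that ends 3 Mar 2017.
3. If the recorded parts, or a stop date, place the event wholly before first dose, keep it non-treatment-emergent.
4. Never impute an onset after the recorded stop date.
5. Reconcile Protocol 15.2 with SAP 3.3.7 on stable pre-existing conditions. Without this, or a recorded indicator of pre-existing status (the documents show none), pre-dose onsets that are blank or share first dose's month or year still count as TEAEs.
6. As secondary wording, state that ongoing AEs receive no imputed stop date, and correct the year-only stop row so that its algorithm matches its example.

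The cost is SAP text and minor programming. Some partially dated events will be assigned to an earlier phase than the true one; for instance, a year-only onset in the year of first dose goes to Day 1. The TEAE count may change slightly in either direction.

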3.3.6. Derived and Transformed Data

Transformations for variables with skewed distributions may be performed as appropriate.

3.3.7. Definitions and Terminology

Adverse Event

An adverse event (AE) is defined as any unfavorable and unintended sign (including an abnormal laboratory finding), symptom or disease temporally associated with the use of a medical treatment or procedure regardless of whether it is considered related to the medical treatment or procedure (attribution of unrelated, unlikely, possible, probable, or definite).

Any medical condition that is present at the time the subject is screened, but does not deteriorate, should not be reported as an AE. However, if it deteriorates at any time during the study it should be recorded as an AE. Hospitalization for elective treatment of a preexisting condition that did not worsen from baseline is not considered an AE or serious AE (SAE).

The descriptions and grading scales found in the revised National Cancer Institute Common Terminology Criteria for Adverse Events (NCI-CTCAE) version 4.03 will be utilized for AE reporting.

Serious Adverse Event

A serious adverse event is any AE that is fatal, life-threatening, requires or prolongs hospital stay, results in persistent or significant disability or incapacity, results in a congenital anomaly or birth defect, or is an otherwise important medical event.

Treatment-emergent AE

Treatment-emergent AEs (TEAEs) are all AEs occurring on or after the date of first dose of study drug through 30 days post the last dose of study drug.

Baseline Value

For purposes of analysis, the baseline value is defined as the last value obtained prior to the first dose of Vicinium.

Study Drug

For the purposes of this study, the term study drug refers to Vicinium.

Day 1 (Baseline)

Day 1 is the day that the first dose of Vicinium is received.

Age

The age of a subject is defined as (Date of Informed Consent – Date of Birth + 1)/365.25.

Study Day

Study Day is defined relative to Baseline (Day 1). Thus, the study day of an event is calculated as:

$$\text{Study Day} = \text{event date} - \text{date of Day 1} + 1.$$

Change from Baseline

Change from baseline for a given endpoint is defined as the Study Day X value minus the Baseline Value.

Cohort 1 Subjects

Subjects with CIS with or without associated papillary disease whose disease is determined to be refractory or relapsed within 6 months of the last dose of adequate BCG treatment. For cohort assignment, 6 months is defined as 28 weeks i.e., 26 weeks (6 months) plus an additional 2 weeks for diagnostic work-up. This group of subjects is identified as Cohort 1 within the eCRF.

Cohort 2 Subjects

Subjects with CIS with or without associated papillary disease whose disease is determined to be refractory or relapsed within 6 months to 11 months of the last dose of adequate BCG treatment. For cohort assignment, 11 months is defined as 50 weeks i.e., 48 weeks (11 months) plus an additional 2 weeks for diagnostic work-up. This group of subjects is identified as Cohort 2 within the eCRF.

Cohort 3 Subjects

Subjects with papillary disease whose disease is determined to be refractory or relapsed within 6 months of the last dose of adequate BCG treatment. For cohort assignment, 6 months is defined as 28 weeks i.e., 26 weeks (6 months) plus an additional 2 weeks for diagnostic work-up. This group of subjects is identified as Cohort 3 within the eCRF.

Adequate BCG Treatment

Adequate BCG Treatment is defined as at least 2 courses of full dose BCG i.e., at least one induction course of at least 5 doses given within 7 weeks, and a second course (maintenance or second induction) of at least 2 doses given within 6 weeks. Full-dose BCG is:

- TICE® BCG: one vial of TICE containing 1 to 8×10^8 colony-forming units (CFU) equivalent to approximately 50 mg (wet weight)
- ImmuCyst® BCG: one vial of ImmuCyst containing 81 mg (dry weight) equivalent to approximately $10.5 \pm 8.7 \times 10^8$ CFU or equivalent.

The “5+2” doses must be completed within 1 year and given to treat the same disease episode with which the subject is enrolling. All subjects must have disease for which the investigator would not treat with additional BCG treatment at the time of enrollment. The determination of adequate BCG will be based on the data in the eCRF.

Treatment-emergent Laboratory Toxicity

A treatment-emergent laboratory toxicity is defined as an increase of at least one toxicity grade from the baseline assessment at any post baseline assessment. For defining treatment-emergent laboratory events, it is assumed that a laboratory assessment obtained on Day 1 with missing collection times occurred prior to the initiation of study drug. If the relevant baseline assessments are missing, then any graded abnormality (i.e., at least Grade 1) is considered as treatment-emergent. For the grading of severity of the laboratory toxicity, the CTCAE v 4.03 will be used.

Concomitant Medications

Concomitant medications are those medications taken on or after the initiation of study drug.

Previous Medications

Previous medications are those medications taken and stopped prior to initiation of study drug.

Treatment Failure

Treatment failure is defined as an event or events that demonstrate the study drug, Vicinium, is not able to achieve or maintain a response in the subject's bladder cancer. Specifically, these events include:

- Subjects whose diagnosis at study entry was CIS or high-grade papillary disease will be considered to have a treatment failure if at the time of any disease status evaluation (per protocol every 13 weeks or any unscheduled evaluation) there is centrally read evidence of high-grade disease (CIS, high-grade Ta or any grade T1 disease) or disease progression (e.g., to muscle invasive disease).
- Low-grade Ta disease is not considered a treatment failure in these subjects and they may remain on study treatment following TURBT. Low-grade Ta disease at the time of evaluation must have the low-grade Ta disease resected.
- Subjects with positive centrally-assessed urine cytology without histologic, cytologic or locally read radiographic evidence of upper or lower urinary tract malignancy will be considered as no longer in complete response and hence, as having a treatment failure.
- Subjects with histologic, cytologic or radiographic evidence of upper or lower urinary tract malignancy will not be considered to have treatment failure but will have study therapy discontinued.
- Subjects who are discontinued due to treatment failure or for recurrence will be considered as treatment failure

Complete Response

Subjects with CIS (Cohort 1 or Cohort 2) will be considered to have a complete response if at the time of any disease status evaluation (per protocol every 13 weeks or any unscheduled evaluation) there is no evidence of high-grade disease (CIS, high-grade Ta or any grade T1 disease) or disease progression (e.g., to muscle invasive disease). Subjects whose initial diagnosis was CIS who are found to have low-grade Ta disease at the time of an evaluation must have the low-grade disease resected by TURBT. Low-grade Ta disease is not considered a treatment failure in these subjects and they may remain on study treatment following TURBT.

Date of Complete Response or Treatment Failure

Given that the cystoscopy, biopsy, and cytology assessments may be conducted on different dates, the date of complete response or treatment failure will be defined as the earliest assessment date of these assessments.

Duration of Response

Duration of Response will be analyzed for subjects with CIS with or without papillary disease (Cohort 1 + Cohort 2) who achieve complete response using a Kaplan-Meier (KM) product-limit method. It is defined as the number of days from the date of first occurrence of complete response to the date of documented treatment failure or death, whichever occurs first. Subjects who do not experience treatment failure or death will be censored at their last assessment of response.

Event

For the purposes of defining Event-Free Survival, an event is defined as treatment failure or death on or prior to treatment discontinuation. Because disease assessments are not recorded after treatment discontinuation, a death after treatment discontinuation will not be counted as an event so as not to artificially inflate EFS. Presence of upper or lower urinary tract urothelial carcinoma and having a cystectomy are not treated as events for analysis but do trigger special data handling in the event-free survival analysis.

Event-Free Survival

EFS is defined as the interval from the date of first dose of study treatment to an event. Subjects who have a treatment failure or die following the post induction visit will be treated as having an event on the date of treatment failure or death. Subjects without evidence of a treatment failure who are diagnosed with upper or lower urinary tract urothelial carcinoma by histology, cytology or radiographic evidence will be censored at the date of diagnosis. Subjects without evidence of a treatment failure who undergo cystectomy will be censored at the date of cystectomy. All other subjects will be censored at the time of last assessment including long-term follow up.

Censoring rules for the analysis of EFS are presented in the table below.

Table: Censoring scheme for EFS

Situation	Date of Event or Censoring	Outcome
Treatment failure	Date of treatment failure	Event
Death without treatment failure and occurring prior to treatment discontinuation	Date of death	Event
Death without treatment failure and occurring after treatment discontinuation	Date of last evaluable disease assessment on or prior to treatment discontinuation ^a	Censored ^a
No baseline disease assessment	Date of first dose	Censored
No on-study disease assessments and no death	Date of first dose	Censored
No treatment failure and no death	Date of last evaluable disease assessment	Censored
New anti-cancer therapy received without treatment failure and reported prior to or on the same day as disease assessment	Date of last evaluable disease assessment on or prior to the date of initiation of subsequent therapy	Censored
Second non-NMIBC cancer reported prior to or on the same day as disease assessment	Date of last evaluable disease assessment on or prior to the date of diagnosis of non-NMIBC cancer	Censored
a This censoring rule acknowledges that disease assessments were not recorded after treatment discontinuation due to an AE.		

Cystectomy-Free Days

Cystectomy-free days is defined as the time from the date of first dose of study treatment to physical removal of the bladder. Subjects who are alive and do not have their bladder removed will be censored at the time of last contact.

Censoring rules for the analysis of cystectomy-free days are presented in the table below.

Table: Censoring scheme for Cystectomy

Situation	Date of Event or Censoring	Outcome
Cystectomy	Date of cystectomy	Event
Death without cystectomy	Date of death	Censored
No cystectomy	Date of last contact	Censored

Time to Disease Recurrence

Time to disease recurrence is defined for subjects in Cohort 3 only as follows:

Time to disease recurrence is defined as the number of days from first dose of study treatment to the first occurrence of treatment failure or death on or prior to treatment discontinuation. Because disease assessments are not recorded after treatment discontinuation, a death after treatment discontinuation will not be counted as an event so as not to artificially inflate time to disease recurrence. Subjects who do not experience treatment failure will be censored at the last assessment on treatment.

Censoring rules for the analysis of time to disease recurrence are presented in the table below.

Table: Censoring scheme for time to disease recurrence in Cohort 3

Situation	Date of Event or Censoring	Outcome
Disease recurrence	Date of disease recurrence	Event
Death without disease recurrence and occurring prior to treatment discontinuation	Date of death	Event
Death without disease recurrence and occurring after treatment discontinuation	Date of last evaluable disease assessment on or prior to treatment discontinuation ^a	Censored ^a
No baseline disease assessment	Date of first dose	Censored
No on-study disease assessments and no death	Date of first dose	Censored
No disease recurrence and no death	Date of last evaluable disease assessment	Censored
New anti-cancer therapy received without treatment failure and reported prior to or on the same day as disease assessment	Date of last evaluable disease assessment on or prior to the date of initiation of subsequent therapy	Censored
Second non-NMIBC cancer reported prior to or on the same day as disease assessment	Date of last evaluable disease assessment on or prior to the date of diagnosis of non-NMIBC cancer	Censored

a This censoring rule acknowledges that disease assessments were not recorded after treatment discontinuation due to an AE.

Progression-free Survival (PFS)

Progression-free survival (PFS) will be analyzed for subjects in Cohorts 1, 2 and 3 and is defined as the time from the date of first dose of study treatment to the date of disease progression (e.g., T2 or more advanced disease) or death on or prior to treatment discontinuation, whichever occurs first. Because disease assessments are not recorded after treatment discontinuation, a death after treatment discontinuation will not be counted as an event so as not to artificially inflate PFS. Subjects without disease progression or death will be censored at the last assessment.

Censoring rules for the analysis of PFS are presented in the table below.

Table: Censoring scheme for PFS in Cohorts 1, 2, and 3

Situation	Date of Event or Censoring	Outcome
Disease progression	Date of disease progression	Event
Death without disease progression and occurring prior to treatment discontinuation	Date of death	Event
Death without disease progression and occurring after treatment discontinuation	Date of last evaluable disease assessment on or prior to treatment discontinuation ^a	Censored ^a
No baseline disease assessment	Date of first dose	Censored
No on-study disease assessments and no death	Date of first dose	Censored
No disease progression and no death	Date of last evaluable disease assessment	Censored
New anti-cancer therapy received without treatment failure and reported prior to or on the same day as disease assessment	Date of last evaluable disease assessment on or prior to the date of initiation of subsequent therapy	Censored
Second non-NMIBC cancer reported prior to or on the same day as disease assessment	Date of last evaluable disease assessment on or prior to the date of diagnosis of non-NMIBC cancer	Censored
a This censoring rule acknowledges that disease assessments were not recorded after treatment discontinuation due to an AE.		

Overall Survival (OS)

Overall Survival (OS) is defined as the time from the date of first dose of study treatment to death due to any cause. Subjects who are alive will be censored at the date of last contact.

Fridericia Corrected QT (QTcF)

$$QTcF = \frac{QT}{\sqrt[3]{RR}}$$

Bazett Corrected QT (QTcB)

$$QTcB = \frac{QT}{\sqrt{RR}}$$

